18.1 ARCHIVING

18.1.1 TRIAL DATA AND DOCUMENTS HELD BY CTRU

At the end of the trial, all data held by the CTRU and all trial data will then be securely archived at the University of Leeds in line with the Sponsor's procedures for a minimum of 5 years. When there is no longer a lawful basis for retaining the data, it will be securely destroyed.

18.1.2. TRIAL DATA AND DOCUMENTS HELD BY RESEARCH SITES

Research sites are responsible for archiving all trial data and documents (ISF and all essential documents therein, including CRFs) at the participating research site until authorisation is issued from the Sponsor for confidential destruction.

18.1.3 PARTICIPANT MEDICAL RECORDS HELD BY RESEARCH SITES

Research sites are responsible for archiving trial participant medical records in accordance with the site's policy and procedures for archiving medical records of patients who have participated in a clinical trial. However, participant medical records must be retained until authorisation is received from the Sponsor for confidential destruction of trial documentation.

19 STATEMENT OF INDEMNITY

The University of Leeds is able to provide insurance to cover for liabilities and prospective liabilities arising from negligent harm. Clinical negligence indemnification for UK sites will rest with the participating NHS Trust or Trusts under standard NHS arrangements.

20 TRIAL ORGANISATIONAL STRUCTURE

Research sites will liaise with the CTRU for advice and support on trial set-up and operation, and submission of trial data. In turn, the CTRU will be responsible for data chasing.

20.1 OPERATIONAL STRUCTURE

Chief Investigator (CI): As defined by the NHS UK Policy Framework for Health and Social Care, the CI is responsible for the design, management and reporting of the trial.

Trial Sponsor - University of Leeds: The Sponsor is responsible for trial initiation management and financing of the trial as defined by the Directive 2001/20/EC. The sponsor delegates some of these responsibilities to CTRU as detailed in the trial contract.

Clinical Trials Research Unit (CTRU): the CTRU at the University of Leeds will have responsibility for the conduct of the trial in accordance with the NHS UK Policy Framework for Health and Social Care and CTRU SOPs. The CTRU will provide set-up and monitoring of trial conduct to CTRU SOPs and the NHS UK Policy Framework for Health and Social Care including randomisation design and service, database development and provision, protocol development, CRF design, trial design, source data verification, ongoing management including training, monitoring reports and trial promotion, monitoring schedule and statistical analysis for the trial. In addition, the CTRU will support ethical approval submissions, any other site-specific approvals, and clinical set-up. The CTRU will be responsible for the overall day-to-day running of the trial including trial administration, database administrative functions, data management, safety reporting, and all statistical analyses. At the end of the trial, CTRU will be responsible for archiving all data and trial data held by the CTRU in line with the Sponsor's procedures for a minimum of 5 years.

Research Sites (local PI): The responsibility for ensuring clinical management of participants is conducted in accordance with the trial protocol ultimately remains with the PI at each research site.

20.2 OVERSIGHT/TRIAL MONITORING GROUPS

Trial Management Group (TMG): the TMG, comprising the CI, CTRU team, other key external members of staff involved in the trial, and a patient representative will be assigned responsibility for the clinical set-up, on-going management, promotion of the trial, and for the interpretation of results. Specifically the TMG will be responsible for:

- Protocol completion
- CRF development
- Obtaining approval from the HRA, UK REC and supporting applications for Site Specific Assessments (SSAs)
- Completing cost estimates and project initiation
- Nominating members and facilitating the TSC and DMEC
- Reporting of complications
- Monitoring of screening, recruitment, treatment and follow-up procedures
- Auditing consent procedures, data collection, trial end-point validation and database development.

Trial Steering Committee (TSC): the TSC will have overall responsibility for the external oversight of the trial. The TSC will provide overall blinded monitoring of the trial, in particular trial progress, adherence to protocol, participant safety and consideration of new information. It will include an independent Chair, not less than two other independent members, and a consumer representative. The CI and other members of the TMG may attend the TSC meetings and present and report progress. The independent Committee will meet annually as a minimum and will consider recommendations made by the independent DMEC.

Data Monitoring and Ethics Committee (DMEC): the independent DMEC will review the safety of participants and ethics of the trial by reviewing interim data during recruitment and follow-up. The DMEC will be comprised of between 3 and 5 independent voting members, at least one of whom will be a statistician, and at least one of whom will be a clinician experienced in the relevant area; one DMEC member will assume the role of Chair. DMEC meetings will consist of an open session to discuss aggregate data with the wider trial team and, a closed session, where data (as agreed and specified in the DMEC Charter) will be presented by randomised group and discussed only with the Trial Statisticians. The Committee will meet annually as a minimum and make recommendation regarding continuation, specifically following the internal pilot phase to the TSC.

Public Patient Involvement (PPI): A PPI representative will sit on the Trial Management Group and there will also be a PPI representative on the Trial Steering Committee. The PPI

representatives will advise on aspects of the trial affecting patient participation and review patient documentation.

20.3 FUNDING

This project is funded by the National Institute for Health and Care Research (NIHR) Health Technology Assessment (HTA) Programme (Grant Ref: NIHR128815).The views expressed are those of the author(s) and not necessarily those of the NIHR or the Department of Health and Social Care.

21 PUBLICATION POLICY

The trial will be registered with an authorised registry, according to the International Committee of Medical Journal Editors (ICMJE) Guidelines, prior to the start of recruitment.

The success of the trial depends upon the collaboration of all participants. For this reason, credit for the main results will be given to all those who have collaborated in the trial, through authorship and contributorship. Authorship decisions will be guided by standard requirements for authorship relating to submission of manuscripts to medical journals. These state that authorship credit should be based only on the following conditions being met (http://www.icmje.org):

- Substantial contribution to conception and design, or acquisition of data, or analysis and interpretation of data
- Substantial contribution to drafting the article or revising it critically for important intellectual content
- Substantial contribution to final approval of the version to be published.

In light of this, the CI, other grant co-applicants, and relevant senior CTRU staff will be named as authors in any publication, subject to journal authorship restrictions. In addition, all collaborators will be listed as contributors for the main trial publication, giving details of roles in planning, conducting and reporting the trial. It is planned that the top five recruiting LaCeS2 research site staff will be named as authors. In addition, LaCeS2 publications will be published on behalf of the LaCeS2 Group. All PIs and associate PIs from participating sites who achieve their minimum recruitment target (12 participants per year) will be included as members of the LaCeS2 Group.

To maintain the scientific integrity of the trial, data will not be released prior to the first publication of the analysis of the primary endpoint, either for trial publication or oral

presentation purposes, without the permission of the TSC. In addition, individual collaborators must not publish data concerning their participants which is directly relevant to the questions posed in the trial until the first publication of the analysis of the primary endpoint.

On completion of the research project a draft final report will be submitted to the HTA programme (trial funder) by the CTRU, within 14 days. This will be peer reviewed and then published on the HTA website. The CTRU is obliged to provide NIHR/HTA with advanced notice of any publication relating to the trial. Copies of any materials intended for publication will be provided to NIHR/HTA at least 28 days prior to submission for publication.

22 QUALITATIVE SUB-STUDY

22.1 PATIENT AND STAFF VIEWS OF THE LACES2 STUDY

22.1.1 BACKGROUND

Our feasibility study was conducted in sites with a strong track record of laparoscopic surgery [10] and we found clinicians could struggle with presenting the trial to some patient groups [31]. Widening recruitment to other sites is likely to identify new recruitment challenges, so LaCeS2 includes integrated qualitative work to prospectively identify and address these challenges in the new sites. It is well recognised that training health professionals to recruit to trials helps recruitment. We also know that each site will have its own challenges and so we will prospectively identify challenges and use the learning from this work, and our previous work to develop a tailored staff recruitment training package to deliver in sites, informed by the Quintet programme [46], [47], [48], [49].

The Quintet programme identified a range of recruitment challenges, such as patient preferences, how to discuss trial terminology (e.g. what is randomisation? Why randomise?), how to provide complex information about trials to different patient groups, gaining authentic informed consent [50]. Our own research also identified other key barriers, including a lack of patient equipoise, a reluctance to approach unwell or complex patients (and reluctance to use patient advocate consent), and more practical issues such as a lack of on-call surgeon, research nurse time, and a lack of experience recruiting to trials, and in smaller centres, access to operating theatres [11]. We anticipate that other challenges will be identified when we talk with new centres, some of which will be new to surgical trials.

In the feasibility study we interviewed patients who consented to participate in the study and identified ways to improve the experience for participants and adapted our study design to

accommodate these changes [31]. Our feasibility work identified reasons patients consented to trial participation, but in the feasibility study there were few trial decliners and none consented to interview, so we have limited understanding of their reasons for declining. Studies show we can learn a lot from trial decliners about how a trial invitation is presented and received, and this knowledge can be used to improve recruitment [51]. Therefore, in this sub-study we will seek to recruit people who decline trial participation to understand their reasons, and if possible adapt our recruitment processes to improve patient experience. As we have made changes to the study design following the feasibility study, we will also seek to interview consenters to ensure that the changes we have made and the recruitment materials we will use in this study are acceptable to patients.

22.1.2 AIM

To understand the trial from the perspective of patients and recruiters and adapt recruitment processes to improve recruitment. These findings will be used to develop a bespoke training package for recruitment staff.

22.1.3 **DESIGN**

Cross-sectional in-depth semi-structured interviews.

22.1.4 ELIGIBILITY AND SAMPLING

22.1.4.1 SITE ELIGIBILITY

All sites recruiting to the LaCeS2 trial will take part in this sub-study.

22.1.4.2 PATIENT ELIGIBILITY

Patients from all sites who consent or decline trial participation during the pilot phase will be eligible to participate.

22.1.4.3 STAFF ELIGIBILITY

Staff involved in LaCeS2 recruitment will be eligible to participate.

22.1.4.4 SAMPLING

A purposive sample of patients approached for the trial will be recruited (10-12 decliners, and up to 30 consenters), where possible representing males and females with a range of ages and clinical presentations.

A random sample of 20-25 staff involved in recruiting to the trial from a range of centres will be recruited. Staff to be sampled include: local principal investigators, research nurses, surgical trainees and other surgeons who will recruit to the study.

22.1.5 RECRUITMENT AND DATA COLLECTION PROCESSES (PATIENTS)

During the internal pilot phase, all patients approached for the trial (decliners and consenters) will be invited to take part in an interview to gather their views on the trial recruitment processes and intervention. Patients may consent immediately, decline immediately, or defer their consent.

If a patient consents immediately, a member of the local research team will forward information to the qualitative research team and arrangements will be made to interview the patient, either while the patient is in hospital, or post-discharge, as appropriate. If a patient defers consent, verbal consent for the qualitative researcher to receive their contact details and to re-approach the patient post-discharge will be sought by the local research team and noted on the recruitment log. Sites will pass patient contact information and copies of participant consent forms (where applicable) to the qualitative research team using a secure drop box facility. In the event that a patient is not approached at all about the sub-study prior to discharge, the local site research team will send out an invitation letter introducing the sub-study to the patient alongside the relevant Participant Information Sheet and an expression of interest form. If the patient is interested in taking part in an interview and is happy to be contacted by a member of the qualitative research team to discuss further, the patient can complete the expression of interest form with their contact details and return this to the qualitative research team either directly by post or via the LaCeS2 research team at their hospital. Alternatively, a member of the local site research team may contact the patient by telephone to confirm that the patient is happy for their contact details to be passed onto the qualitative research team.

The qualitative researcher will contact all patients who consent or agree to contact by phone or post, as appropriate. Any patients who verbally give consent to contact and agree to take part in the sub-study, will be asked to sign a consent form wherever possible; if it is not possible for the patient to sign the consent form prior to the date of the interview e.g. because of COVID-19 restrictions, verbal consent will be taken at the start of the interview instead, and the section of audio file that goes through the consent process will be saved.

Trial decliners and consenters who consent to interview will be invited to participate in a faceto-face, telephone or video chat interview (depending on patient preference and COVID-19 restrictions). Interviews will be guided by a topic guide developed for the study to explore their response to the trial invitation, and the information materials provided to them, in order to

understand their decision, and improve trial processes. Interviews are likely to take place post-discharge, but researchers will be flexible to patient wishes (e.g. if patients wish to be interviewed whilst still in hospital this will be accommodated, if feasible).

22.1.6 RECRUITMENT AND DATA COLLECTION PROCESSES (STAFF)

Staff will be recruited via the local principal investigator, with support from local R&D offices. All sites will be aware of their involvement in the trial prior to contact being made with the local principal investigator. A participant information sheet explains the qualitative study and invites the team to identify team members for interview. Interview respondents will be selected from those who respond to the interview invitation and will be selected to ensure the following characteristics are represented: new/experienced recruiters; junior/senior staff; nurses and doctors.

Telephone/online interviews will take place during the internal pilot phase. Interviews will use a topic guide informed by the findings of our feasibility study [11] and the Quintet intervention [50] to assess their knowledge of the evidence base for laparoscopic surgery, their understanding of equipoise, and generate a discussion of the recruitment materials and how the pathway and protocol fit with their clinical practice. The interviewer will identify local level recruitment barriers and work with sites to put in place potential solutions that can be implemented locally.

22.1.7 DATA ANALYSIS

Interviews will be audio-recorded, with participant permission, and transcribed verbatim. Transcripts will be anonymised at point of transcription. NVivo qualitative data analysis software will be used to store and manage the transcripts during analysis. Deductive thematic data analysis will be undertaken with transcripts coded by ascribing words and phrases to capture the meaning in the text to identify common emerging ideas [52]. To ensure reliability in the coding a subset of transcripts will be dual coded by two researchers and any discrepancies discussed until consensus reached. A coding index will be developed using the first five transcripts and applied to the remaining transcripts. The analysis will focus on identifying recruiter and patient attitudes or behaviours that are amenable to change, and views of the recruitment materials. One researcher will lead on the analysis, with regular meetings with the qualitative lead and Chief investigator overseeing the process. The analysis will be undertaken in parallel with data collection so data analysis can inform later sampling decisions and interview questions.

22.1.8 OUTPUTS

Emerging findings will be fed back to the TMG and all sites in an ongoing manner, to aid recruitment during the pilot study, and additional training for staff implemented, if needed. Findings will be reported to the DMEC at the end of the pilot phase to inform DMEC recommendations at that time.

Findings from the staff interviews will be used along with data from our feasibility study to help develop a training programme which will be delivered to local research site staff at each site, throughout the trial to refresh their training, and offer training to new staff joining the trial (see section 23.3 for further details).

Staff training will be offered as face-to-face or telephone support. If, in the light of COVID, face-to-face training is not possible, an online training resource will be developed using a combination of pre-recorded presentations and online discussions.

23 STUDY WITHIN A TRIAL (SWAT)

Emergency surgery trials have been regarded to be difficult to run due to a number of perceived difficulties including acceptable recruitment, timely randomisation, attrition, safety and clinician and patient equipoise. The timely delivery of definitive clinical care to an unwell cohort of patients must be prioritised over trial-related processes. To address some of the practical and logistical issues associated with running surgical trials in the emergency setting a SWAT will be carried out to examine strategies to maximise efficiency in emergency surgery trials.

23.1 INTEGRATION OF ROUTINE DATA

An assessment of the feasibility, quality and accuracy of collecting trial-related data from routine data from the National Emergency Laparotomy Audit (NELA) will be undertaken. Case report forms (CRFs) are currently considered the gold standard for collecting trial-specific data and the LaCeS Feasibility Trial reported a data compliance rate of over 95% for the operative CRF. The aim of this study is to externally validate the use of NELA as a data collection platform for surgical trials by comparing its data ascertainment and accuracy with the standard trial CRFs for all LaCeS2 participants recruited at sites in England and Wales.

23.2 OPTIMISING RECRUITMENT STRATEGIES IN THE EMERGENCY SETTING

During the LaCeS2 recruitment period, we will try to identify the most effective method(s) of recruitment. Recruitment strategies may include videos, patient stories & clinician-led recruitment, with sites receiving one or more of these interventions. The impact of these strategies will be analysed quantitatively by evaluating recruitment rates, and the implementation and acceptability of these strategies may also be evaluated qualitatively through other aspects of the embedded qualitative work. Where relevant, the findings of this study will feed into the development of the evolving site training package, which will be used to provide additional recruitment support to sites on an ongoing basis throughout the trial (see section 23.3).

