23.3 SITE TRAINING PACKAGE

An emergency-trial-specific training package for local research teams to help them identify, approach and recruit patients will be developed and delivered to sites at site opening and on an ongoing basis throughout the recruitment period. The initial training package will be informed by the findings of the LaCeS Feasibility Trial but this training will be updated as the trial progresses based on emerging findings from other aspects of the embedded qualitative work e.g. interviews with trial consenters and decliners (section 22), site staff interviews (section 22) and the evaluation of effective recruitment strategies (section 23.2).

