Grade IV	 Any deviation from the ideal intraoperative course With the need for any additional major and urgent treatment or intervention Patient with life-threatening symptoms and/or leading to permanent disability 	 Bleeding: Life-threatening bleeding with splenectomy; massive blood transfusion; ICU stay Injury: Injury of central artery or vein requiring extended intestinal resection Cautery: Life-threatening burn injury by cautery leading to fire requiring ICU treatment Arrhythmia: Arrhythmia requiring electroconversion, defibrillation or admission to the ICU
Grade V	Any deviation from the ideal intraoperative course With intraoperative death of the patient 	

¹ The following events are not defined as intraoperative adverse events: sequelae, failures of cure, events related to the underlying disease, wrong-site or wrong-patient surgery or errors in indication

Appendix 5 - SWAT Protocol: Infographic Study Within the LaCeS2 Trial (part of the Optimising Recruitment Strategies in the Emergency Setting SWAT, see section 23.2 OPTIMISING RECRUITMENT STRATEGIES IN THE EMERGENCY SETTING)

Sustained recruitment of patients at an anticipated rate is crucial to the successful delivery of randomised clinical trials (1). Various reviews suggested that achieving the required sample size remains a constant challenge for nearly half of randomised trials (2-4). Particularly, emergency surgery trials struggle to recruit participants due to the serious nature of the medical condition as well as the complex demands of the setting. The reduced time between approaching eligible patients and randomisation, and clinician and patient equipoise also add to these challenges.

Infographics are known to have helped in improving patient knowledge in relation to discharge instructions, and statistical association of cancer risk and old age (5) (6). Infographics provide key trial information in a graphical format, so can be easier to understand than text, especially in stressful situations, and by those with lower literacy levels. A study by Buljan and colleagues showed that study participants preferred an infographic to a text-based plain language summary and this was associated with a more positive reader experience and perceived user-friendliness of the information sheet (7). These findings demonstrate the potential benefits of infographics in making randomised trials accessible for patients, and allowing patients to make an informed decision about trial involvement.

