We plan to run a Study Within A Trial (SWAT) during the LaCeS2 recruitment period. The objective of this SWAT is to try to maximise efficiency in patient recruitment using an Infographic Sheet (visual document explaining the study). LaCeS2 sites will be randomised to receive the Infographic Sheet plus the standard Patient Information Sheet (PIS) versus a standard PIS only.

The sample size is constrained by the number of potential participants approached and recruitment into the host trial, hence a formal power calculation to determine the sample size has not been conducted.

SWAT study design

The embedded SWAT study design will be a cluster trial; randomisation will be carried out at the site level to reduce cross contamination.

The sample size will be dependent on the LaCeS2 host trial. The LaCeS feasibility trial had an overall mean steady-state recruitment rate at 1.2 patients per month per site, and a more conservative recruitment rate of 0.65 patients per site per month is expected for the LaCeS2 trial. All sites will be approached to take part in the SWAT. The intervention is a recruitment infographic which includes visual information about the purpose of the trial, treatments options, risks and benefits of treatment options, and the randomisation process.

The primary outcome of this embedded SWAT study will be on the recruitment rate to the trial and it will not affect the host-study results. Eligible participants will not be aware of the SWAT, but staff will be aware of the addition of the infographic. The SWAT infographic has been designed in collaboration with two patient representatives on the trial committee and will be submitted to an ethics committee for ethical approval prior to use.

SWAT data analysis

The hypothesis that the use of the infographic will help in increasing the recruitment rate into the host trial will be analysed quantitatively at the end of the study by evaluating recruitment rates and we may also qualitatively assess the implementation and acceptability of the infographic through other aspects of the embedded qualitative work.

SWAT study output

The results of this SWAT will contribute to the evidence about the recruitment strategy of using infographics in clinical and academic research.

References:

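### Sections 23.2 and 23.3 let findings on the infographic SWAT enter in-trial site training, with no exception protecting the sites randomised to the standard information sheet only

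*Protocol*

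**What the plan says.** **The comparison.** Appendix 5 sets out a cluster-randomised SWAT in which sites receive either the infographic with the standard PIS or the PIS alone. The reason given for the unit of allocation is that "randomisation will be carried out at the site level to reduce cross contamination". The primary outcome is the recruitment rate to the host trial, and the hypothesis "will be analysed quantitatively at the end of the study". The title of the appendix describes the infographic study as "part of the Optimising Recruitment Strategies in the Emergency Setting SWAT, see section 23.2".

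**The training rule.** Section 23.2 says that, where relevant, "the findings of this study will feed into the development of the evolving site training package", and that this package will give "additional recruitment support to sites on an ongoing basis throughout the trial". Section 23.3 says that "this training will be updated as the trial progresses based on emerging findings from other aspects of the embedded qualitative work", and its list of sources includes "the evaluation of effective recruitment strategies (section 23.2".

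**The feedback rule.** Section 22.1.8 adds, for the qualitative sub-study, that "Emerging findings will be fed back to the TMG and all sites in an ongoing manner". It gives helping recruitment during the pilot as the purpose. Appendix 5 allows the infographic's implementation and acceptability to be assessed through that same qualitative work, as an option.

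**The concern.** Site-level randomisation protects the comparison only if PIS-only sites stay unexposed to the infographic and to what is learned from it. The training package is a channel that runs to sites throughout recruitment, and the evaluation containing the infographic study is one of its named inputs. If infographic messages travel along it, recruiters at PIS-only sites may start to explain the trial as the infographic does. The two arms then become more alike for the rest of recruitment, and an infographic that works could be reported as making little difference.

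Only the SWAT's own conclusion is at stake. The host trial randomises individual patients between laparoscopic and open surgery, and its 30-day complication comparison does not depend on which recruitment material a site used.

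**Working it through.** The protocol states no figure for the SWAT that could be reproduced. The check is therefore a reading of the sections against each other, followed by the direction of the bias.

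**1. Does the training rule cover the infographic?** Yes. Section 23.2 refers to the findings of the recruitment-strategy study, and the title of Appendix 5 places the infographic study inside it.

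**2. Who receives the training, and when?** Sections 23.2 and 23.3 speak of sites in general and of delivery during recruitment. Appendix 5 says that all sites will be approached for the SWAT. PIS-only sites are therefore among the recipients, and nothing exempts them.

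**3. Which findings could exist before the end?**
- *Quantitative.* The analysis is set for the end of the study and no interim look is provided for. It is open whether this means the end of the SWAT or of the host trial, but no earlier SWAT end is given and its sample size is tied to host recruitment.
- *Qualitative.* These could emerge earlier. Section 23.2 and Appendix 5 both allow acceptability and implementation to be assessed qualitatively, and staff know of the infographic. Section 23.3 updates training on emerging findings and counts the 23.2 evaluation among their sources.

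**4. Does any sentence hold infographic findings back?** None was found in 22.1.8, 23.2, 23.3 or Appendix 5.

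**5. Direction of the bias.** Let RR be the true ratio of recruitment rates (infographic to PIS-only), and c the share of PIS-only recruitment time in which those sites perform as infographic sites do. Relative to an unexposed rate of 1, the PIS-only rate averages (1 − c) + c·RR, so

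observed ratio = RR / [(1 − c) + c·RR].

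For any c between 0 and 1 this lies between RR and 1. The shift is always toward no difference. On assumed values, none of them in the documents:

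| Assumed RR | c = 0.25 | c = 0.50 |
|---|---|---|
| 1.2 | 1.2/1.05 = 1.14 | 1.2/1.10 = 1.09 |
| 1.5 | 1.5/1.125 = 1.33 | 1.5/1.25 = 1.20 |

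These values suppose full uptake once a site is exposed. A training update would probably achieve less, which corresponds to a smaller c. The table shows the direction and shape of the bias and does not estimate it for this SWAT.

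**The case against.** The strongest reply is that the sections can be read together without conflict, and much of it stands.

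- **The rules are compatible.** A reader might infer that the training rule and the end-of-study analysis cannot both be followed. The text does not support that. Section 23.2 covers several strategies, naming videos, patient stories and clinician-led recruitment, and the words where relevant leave the team free to withhold infographic findings. Findings on other strategies and from interviews can update training while the infographic comparison waits.
- **The qualitative route is limited.** Assessing the infographic qualitatively is optional. The feedback in 22.1.8 is aimed at the pilot, and sections 22.1.5 and 22.1.6 place the patient and staff interviews in the pilot phase.
- **Exposure is possible, not planned.** A reader might infer that PIS-only sites will be given or taught the infographic. No section says so. Allocation decides which sheet a site uses, and hearing about acceptability does not put the sheet in front of patients.
- **No loss of power can be quoted.** Appendix 5 says that no formal power calculation was done and gives neither an effect size nor an intracluster correlation. Any before-and-after power figure would rest wholly on outside assumptions.

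What remains is narrower. The discretion comes with no rule for using it, the 23.2 evaluation is expressly listed as a training input, and the limits in section 22 do not apply to the training updates in 23.2 and 23.3, which continue through recruitment.

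**Conclusion.** The point holds as a gap in wording. Applied to the infographic, the training rule permits emerging findings, mainly qualitative ones, to reach PIS-only sites before the end-of-study analysis. This works against the safeguard for which Appendix 5 chose site-level randomisation.

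Any effect would be toward no difference. That direction rests on one assumption: that what reaches PIS-only sites moves their recruitment toward that of the infographic sites. Its size cannot be derived from the documents.

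The severity is minor. The SWAT is embedded and has no formal power calculation, and Appendix 5 says that it will not affect the host-study results, with which this check agrees. The point is worth acting on because the change is cheap and contamination cannot be undone at the analysis stage.

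**What to change.** Add to sections 23.2 and 23.3 a sentence such as:

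*Quantitative and qualitative findings on the infographic will not be used in site training or fed back to sites until the end-of-study SWAT analysis. Each site keeps its allocated recruitment material until recruitment closes.*

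In section 22.1.8, make the same exception to the feedback given to sites. Findings on other recruitment strategies, and from the staff, consenter and decliner interviews where they do not concern the infographic, continue to update training as planned.

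The cost is protocol wording only. The one practical downside is that an infographic that looks promising cannot be rolled out early to PIS-only sites.
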